8.5.3.6 Body composition

Changes in baseline in the below body composition parameters at each visit will be analysed using ANCOVA in the same manner as the change from baseline in Tr.vBMD (radius) on HRpQCT (see Section 8.5.2.1):

- Body height
- Body weight
- Body Mass Index (BMI)
- Lean body mass
- Fat body mass

8.5.3.7 Bone Turnover Markers and Metabolic Biomarkers

Changes in baseline in the below bone turnover markers and metabolic biomarkers (and their log transformed values) at each visit will be analysed using ANCOVA in the same manner as the change from baseline in Tr.vBMD (radius) on HRpQCT (see Section 8.5.2.1):

- Parathyroid hormone [PTH]
- Aminoterminal propeptide of type 1 procollagen [PINP]
- Carboxy-terminal propeptide of type 1 procollagen [PICP]
- Osteocalcin [OC]

- Bone-specific alkaline phosphatase [BSAP]
- Carboxy-terminal telo-peptide [CTX-1]
- Amino-terminal telo-peptide [NTX-1]
- Receptor activator of nuclear factor kappa-B ligand [RANKL]
- Osteoprotegerin
- Transforming growth factor beta [TGF- β]
- Sclerostin
- Released C-terminal pro-peptide of Type V collagen [Pro-C5]
- neo-epitope of MMP-2
- 9 mediated degradation of Type V collagen [C5M]

8.5.3.8 PRO's and QoL

All PRO and QoL analyses below will be performed on the FAS and Non-restricted FAS Populations.

8.5.3.8.1 SF-12

Changes from baseline in the norm-based 8 domains scores and 2 component score of the SF-12 at each visit during the treatment period will be analysed using ANCOVA in the same manner as the change from baseline in Tr.vBMD (radius) on HRpQCT (see Section 8.5.2.1).

8.5.3.8.2 EQ-5D-5L

Changes from baseline in the EQ-5D-5L index score and VAS score at each visit during the treatment period will be analysed using ANCOVA in the same manner as the change from baseline in Tr.vBMD (radius) on HRpQCT (see Section 8.5.2.1).

8.5.3.8.3 OIQoL-A

Changes from baseline in the OIQoL-A total score, pain subscale score and activity subscale score at each visit during the treatment period will be analysed using ANCOVA in the same manner as the change from baseline in Tr.vBMD (radius) on HRpQCT (see Section 8.5.2.1).

8.5.3.9 Fractures

All fracture analyses below will be performed on the FAS, Non-restricted FAS and PP populations utilising the X-day data.

The number and proportion of patients with at least one new Peripheral, Vertebral, Non-Vertebral, Long-bone or any fracture will be summarised by treatment group and OI type at Month 12 and presented as the annualised fracture rate. In addition, each quarters fracture rate and the cumulative fracture rate by month will be presented. For each rate, a P-value for the comparison between each group will be provided using a Chi squared test.

Graphs of the cumulative fracture rate by month will be presented.

The time to first fracture will be analysed for each fracture category using Kaplan-Meier methods as per Section 8.5.1. As per Section 7.1.3 patients who do not have a fracture will be censored at the date of completion/discontinuation of the treatment period for each category.

Quartiles for the median time to event will be presented together with their 95% confidence intervals. A Kaplan-Meier plot will also be presented. Comparisons between treatment regimens will be performed by means of the log-rank test.

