- Participants will have HRpQCT scans of their non-dominant distal radius at baseline, 3-month (for open-label participants only), 6-month and 12-month time points to determine the effect of treatment on Tr. vBMD with the primary analysis and dose determination being made after all enrolled patients have completed their 12-month HRpQCT scan.
- Other investigations include study of sparse PK, monitoring for safety and tolerability including immunogenicity, and measurement of the effect of treatment on bone quality, fractures, QoL and utilisation of resources e.g. physical aids and hospitalisation.
- Following completion of the study treatment participants will enter 12 months follow-up and will have visits at Months 14, 18 and 24. Participants will also receive follow-up telephone calls at Months 16 and 21.
- During the follow-up period all participants will have the option to receive zoledronic acid at Month 12 and Month 18 at the discretion of their treating physician.
- During the follow-up period participants will have HRpQCT scans of their non-dominant distal radius and tibia at Month 18 and Month 24.
- For the purposes of the study protocol 1 month is defined as 28 days.
- An Independent Data Monitoring Committee will monitor safety throughout the study and make recommendations on the selected dose.

MBPS205 Study Schematic

Number of Participants:

The number of participants is based on power considerations for the trabecular vBMD (radius) derived from HRpQCT at Month 12. The primary analysis method for this endpoint will be on the change from baseline within each treatment group, so the primary hypothesis to be tested is

$$H_0: \mu_T \leq 0 \text{ vs. } H_1: \mu_T > 0$$

where μ_T denotes the change from baseline for each dose of Setrusumab. Under the assumptions of a maximum change from baseline of [REDACTED], a standard deviation at both timepoints of [REDACTED] and a correlation between both measurements of [REDACTED], a sample size of 25 patients per group yields approximately 80% power for a one-sided test with significance level 0.025, if the data are analysed on the log scale using a t-test.

For a change from baseline of [REDACTED], with standard deviation as above the one-sided test would have a probability of 80% to yield a p-value below 5%, being considered indicative of a trend.

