Secondary	
 • Tr. vBMD (tibia): An ANCOVA will be calculated on log transformed data as described above on the FAS, mFAS, the PP population, the FAS and the Non-Restricted FAS in both versions • DXA BMD: Changes will be compared treatment groups using an ANCOVA as described above on the percent change from baseline and on the T-scores for the following variables on the FAS, the PP population, the FAS and the Non-Restricted FAS in both versions: 
 ○ Lumbar BMD ○ Whole body BMD ○ Proximal femur BMD • Vertebral assessments: 
 ○ Vertebral fractures assessed by Genant's semi-quantitative method: 
 ▪ 2x2 table analysis for occurrence of new and new or worsening fractures (yes/no) ▪ Poisson regression for number of new and new or worsening fractures, if appropriate

Endpoint	Statistical Analysis Methods
	
 ▪ Shift tables to investigate the change in grade for existing fractures ▪ An ANCOVA with baseline value as covariate and treatment group and stratum as factors to investigate the percent change from baseline in numbers of vertebral fractures ▪ An ANCOVA with baseline value as covariate and treatment group and stratum as factors to investigate the total sum of vertebral gradings 
 ○ Vertebral height derived from 6-point quantitative morphometry: The maximum change from baseline in the H_A/H_P and the H_M/H_P ratio for fractured vertebrae will be analysed using ANCOVA • Change in bone histomorphometry • HRpQCT parameters: 
 ○ Total vBMD ○ Cortical vBMD ○ BV/TV ○ Met/Inn ○ TbTh ○ TbN ○ Inhomogeneity ○ Cortical thickness ○ Cortical porosity (tibia and radius) • Body composition: Comparisons between treatment groups will be performed using an ANCOVA as described above 
 ○ Body height ○ Body weight ○ BMI ○ Lean body mass ○ Fat body mass • Change from baseline to each visit for bone turnover markers and metabolic biomarkers • Fracture rate: Chi square tests will be calculated to assess differences across treatment groups on the following on the FAS, the PP population, the FAS and the Non-Restricted FAS in both versions: 
 ○ Total fracture rate ○ Peripheral fracture rate

Endpoint	Statistical Analysis Methods

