4.2 Secondary endpoints

The secondary efficacy endpoints of this study are:

1. Tr. vBMD (radius) on HRpQCT at 12 months.
2. Tr. vBMD (tibia & radius) on HRpQCT and bone strength on FEA at 6 months
3. Tr. vBMD (tibia & radius) on HRpQCT and bone strength on FEA at 3 & 6 months in the open-label treatment arm
4. Total fracture rate at 12 months
5. Peripheral fracture rate at 12 months
6. Vertebral fracture rate at 12 months
7. Long-bone fracture rate at 12 months
8. Changes in vertebral fractures and vertebral height with Genant's semi-quantitative method and 6-point quantitative morphometry from baseline at 6 and 12 months
9. Changes in lumbar, whole body, and proximal femur DXA BMD (dual-energy x-ray absorptiometry bone mineral density) (absolute and T-score) from baseline at Month 6 and Month 12
10. Changes in bone histomorphometry
11. Tr. vBMD (tibia & radius) on HRpQCT and bone strength on FEA at 18 and 24 months
12. Changes (tibial and radial) in Total vBMD, cortical vBMD, bone volume fraction (BV/TV), peripheral to medullary trabecular bone density ratio (Met/Inn), trabecular thickness (TbTh), trabecular number (TbN), inhomogeneity, cortical thickness, and cortical porosity from baseline at 6, 12, 18, and 24 months
13. Changes in Tr. vBMD (tibia) from baseline at 12, 18, and 24 months
14. Changes (tibial and radial) in Total vBMD, cortical vBMD, bone volume fraction (BV/TV), peripheral to medullary trabecular bone density ratio (Met/Inn), trabecular thickness (TbTh), trabecular number (TbN), Inhomogeneity, cortical thickness, and cortical porosity on HRpQCT and bone strength on FEA at 3 months in the open-label treatment arm.
15. Changes in body height, weight and body mass index (BMI) from baseline at 6 and 12 months
16. Changes in lean and fat body mass from whole body DXA

17. Changes from baseline at each visit in bone turnover markers and metabolic biomarkers associated with bone including:
 - Parathyroid hormone [PTH]
 - Aminoterminal propeptide of type 1 procollagen [P1NP]
 - Carboxy-terminal propeptide of type 1 procollagen [P1CP]
 - Osteocalcin [OC],
 - Bone-specific alkaline phosphatase [BSAP]
 - Carboxy-terminal telo-peptide [CTX-1]
 - Amino-terminal telo-peptide [NTX-1]
 - Receptor activator of nuclear factor kappa-B ligand [RANKL]
 - Osteoprotegerin
 - Transforming growth factor beta [TGF- β]
 - Sclerostin
 - Released C-terminal pro-peptide of Type V collagen [Pro-C5]
 - Neo-epitope of MMP-2

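### SAP 8.5.3.9 labels the proportion of patients with at least one fracture by Month 12 an annualised rate, with no annualisation formula and no fixed denominator for early leavers

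*SAP*

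**What the plan says.** SAP 4.2 lists the endpoints as rates, for example "Total fracture rate at 12 months", with matching entries for peripheral, vertebral and long-bone fractures. Neither document defines the rate as events per person-time or as a proportion. Protocol 11.3.1 pairs it with a test of proportions: "Chi square tests will be calculated to assess differences across treatment groups".

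SAP 8.5.3.9 supplies the measure: "The number and proportion of patients with at least one new Peripheral, Vertebral, Non-Vertebral, Long-bone or any fracture will be summarised by treatment group". The Month 12 figure is "presented as the annualised fracture rate". The shorter windows get the same name: "each quarters fracture rate and the cumulative fracture rate by month will be presented". For each of them, "a P-value for the comparison between each group will be provided using a Chi squared test". The section names its populations (FAS, Non-restricted FAS and PP) and describes its source only as "utilising the X-day data".

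Several other places bear on the point:
- Protocol 6.1: "For the purposes of the study protocol 1 month is defined as 28 days".
- SAP 8.1.3 lets categorical summaries use either the non-missing count or the population count, on observed cases.
- SAP 7.1.3.3 and 8.5.3.9 plan Kaplan-Meier and log-rank analyses of time to first fracture, censoring fracture-free patients when they complete or stop the treatment period.
- SAP 8.5.1 sends count variables to Poisson regression with a log-exposure offset, or to negative binomial regression if overdispersed. For fractures, only 8.5.3.3.1 (radiographic vertebral fractures) calls that model.
- SAP 8.6.1 and 8.6.1.1 count repeat fractures as adverse events of special interest, by preferred term, without person-time. SAP 8.6 rules out testing there.

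**The concern.** An annualised fracture rate is normally read as fractures per patient-year. The quantity specified is the share of patients with one or more fractures in a 336-day window. Three things separate the two:
- A patient with three fractures contributes the same as a patient with one.
- The window is shorter than a year, and no scaling rule is given.
- A patient who leaves early without a fracture is neither weighted by time at risk nor clearly placed in or out of the denominator.

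A reader could take the figure as lower than the true event rate, or compare it with person-time rates from elsewhere. Two programmers could also produce different proportions, and different chi-square p-values, from the same data.

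**Working it through.** The documents state no fracture rate, dropout rate or fracture power, so there is no planned figure to reproduce. The rates, stratum mix, dispersion and dropout below are assumptions.

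**Window.** 12 × 28 = 336 days. The SAP 7.1.4.2 exposure formula agrees: the last infusion at Month 11 falls 11 × 28 = 308 days after the first dose, and 308 + 28 = 336. As a fraction of a year, t = 336/365.25 = 0.920. Scaling to a year would need a factor of 365.25/336 = 1.087 even for completers.

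**Proportion against rate, full follow-up.** For a stratum rate λ and dispersion a, P(at least one fracture) = 1 − exp(−λt) if a = 0, and 1 − (1 + aλt)^(−1/a) otherwise. The strata are weighted 70% Type I and 30% Type III/IV, with a from 0 to 1.

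Example with rates 0.14 and 0.34, so the mean is 0.7 × 0.14 + 0.3 × 0.34 = 0.20:
- a = 0: 0.7 × 0.1208 + 0.3 × 0.2686 = 0.165
- a = 1: 0.7 × 0.1141 + 0.3 × 0.2383 = 0.151

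The uncounted share is 1 − P/(mean rate × t).

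| True rate per patient-year (Type I / III-IV) | Proportion shown | Fractures not counted |
|---|---|---|
| 0.10 (0.07 / 0.17) | 0.083-0.087 | 5-10% |
| 0.20 (0.14 / 0.34) | 0.15-0.17 | 10-18% |
| 0.39 (0.3 / 0.6) | 0.26-0.30 | 17-28% |
| 1.16 (0.8 / 2.0) | 0.49-0.62 | 42-54% |

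**If the word annualised implied a formula.** Taking −ln(1 − P)/t gives 0.094-0.099 for a true 0.10, 0.18-0.20 for 0.20 and 0.325-0.382 for 0.39. That closes much of the gap, but the SAP gives neither this formula nor any other.

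**Denominator.** Assume 20% leave, uniformly over 336 days. Let R be the full-window risk and R̄ its average over leaving times. Counting every patient gives A = 0.8R + 0.2R̄. Dropping fracture-free leavers gives A/(0.8 + 0.2R̄).
- At 0.20 per year: 14-15% against 17-18%. The full-window risk, which Kaplan-Meier estimates, is 15-17%.
- At 0.80 per year (0.5 / 1.5): 36-44% against 43-52%, with full-window risk 39-48%.

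**Invented arm.** Take 25 patients, 5 leaving at day 168, and 12 fractures in 8 patients. Person-time is (20 × 336 + 5 × 168)/365.25 = 20.7 years. The rate is 12/20.7 = 0.58 per patient-year, with an exact 95% Poisson interval of 0.30 to 1.01 (chi-square quantiles 12.40 on 24 df and 41.92 on 26 df, each divided by 2 × 20.7). The SAP figure would be 8/25 = 32%, or 8/20 = 40% if the five leavers had no fracture and were dropped.

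**The case against.** The sentence itself says it is a proportion of patients with at least one fracture, so a careful reader is not misled. Kaplan-Meier with log-rank, in the same section and by fracture category, already handles early leaving. The populations are named and fractures are assessed continuously, so the population count is the natural denominator. Chi-square is the protocol's choice. With 25 patients per arm, a 30% proportion has a 95% interval of about ±18 points (1.96 × √(0.3 × 0.7/25)), against which a denominator effect of about 3 points at 0.20 per year is small. Most of this stands, and it limits the point. It does not justify the rate label or remove the choice that SAP 8.1.3 leaves open.

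Four stronger readings are tempting, and the documents do not support them:
- **The fracture source is undefined.** Protocol 10.1.1.3 specifies fractures confirmed by central radiographic reading, excludes those without clinical symptoms, and fixes the event date. The SAP wording is most likely a slip for X-ray.
- **The plan ignores early leaving and repeat fractures.** Kaplan-Meier covers early leaving for the first fracture. The adverse-event tables count repeats, and 8.5.3.3.1 models counts of radiographic vertebral fractures.
- **Dose ratios will be pulled toward 1.** SAP 8.5.3.9 plans proportions and p-values. It plans no ratios of these proportions and no summing of quarters.
- **Every category needs a rate-ratio model.** In simulation (two arms of 25, 15% leavers), one arm had no fractures in 22-26% of comparisons at 0.10 per year. A stratified Poisson or negative binomial model fitted regardless rejected a true null in 3.7-11.5% of trials across 0.10 to 1.16 per year. Chi-square gave 3.9-6.6% over a slightly smaller set of scenarios. Such a model would also give vertebral fractures a second count analysis.

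**Conclusion.** The point holds as one of labelling and specification. Followed as written, SAP 8.5.3.9 reports a once-per-patient cumulative risk over 336 days under the name of an annualised rate, without a formula, and with a denominator that can be read two ways. Annualisation is named but unspecified, which is different from being ruled out.

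The size depends on fracture rates that the documents do not give. Eligibility requires only one fracture in 5 years (Protocol 7.1), so low rates are plausible, and there the gap is small. The large gaps need assumed rates near one fracture per patient-year. The calculations further assume 70% Type I, gamma-Poisson counts with dispersion 0 to 1 and, for the denominator, 20% leavers.

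The affected results are secondary comparisons between active doses without multiplicity adjustment (SAP 8.1.4). The primary Tr. vBMD conclusion is not affected. The text should still be corrected, because the label is wrong whatever the fracture rate and the correction is cheap.

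**What to change.** In SAP 8.5.3.9:

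1. Relabel the 12-month, quarterly and monthly figures as the proportion of patients with at least one fracture in the stated window, and say that Month 12 is 336 days.
2. Keep the protocol's chi-square test for the proportion, with a fixed denominator: all patients in the named analysis population, with fracture-free early leavers counted as having no fracture. Beside it, give the Month 12 estimate from the planned Kaplan-Meier analysis as the figure that accounts for early leaving. It should accompany the fixed denominator and not replace it, because chi-square needs one.
3. If an annualised rate is reported, calculate it as total fractures divided by patient-years under observation, from the 7.1.3.3 start to the end of the treatment period, by arm and category, with exact Poisson intervals. Record the addition in SAP section 9. A rate-ratio model as in 8.5.1 is optional and exploratory, only where both arms have fractures. For vertebral fractures its offset should be aligned with 8.5.3.3.1.
4. Correct the source wording and refer to the centrally confirmed symptomatic fractures of Protocol 10.1.1.3.

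Items 1 and 4 are wording only. Item 2 is wording plus one line of output, since the SAP lists only quartiles and a plot from Kaplan-Meier. Item 3 takes a little programming. Its intervals will be wide in sparse categories and somewhat too narrow where repeat fractures cluster within patients, which a footnote can state.

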3.2 Randomisation and blinding

3.2.1 Randomisation

All participants will be centrally randomised using an Interactive Web Response System (IWRS) in a 1:1:1:1 ratio to receive either 20mg/kg, 8mg/kg, 2mg/kg or open-label 20 mg/kg stratified by OI type (Type I or III/IV). Subject to informed consent being given by the participant, all participants assigned to placebo prior to protocol amendment 4.0 will be reassigned to begin 12 months of open-label 20 mg/kg setrusumab treatment. ICON Biostatistics will produce a randomisation list that links participant numbers to randomisation numbers. These randomisation numbers will be linked to different treatment regimens and the randomisation scheme will be stratified according to the Sillence Clinical Classification of OI type into 2 groups (Type I or III/IV).

Following confirmation from the investigator, the pharmacist will contact the IWRS and be issued with a treatment regimen. Should the participant be allocated to a setrusumab regimen, then the pharmacist will input the patient's weight into the IWRS and receive a calculated dose per participant.

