8.5.1 Analysis methods

For all continuous outcomes, where appropriate, an ANCOVA model analysis will be performed. Analyses will include the fixed, categorical effects of treatment and randomisation stratum as well as the associated baseline value as a covariate. Significance tests for treatment differences (between Setrusumab doses) will be based on least-squares means (LSMeans).

ANCOVA analyses dealing with nested observations within a patient (e.g., vertebral assessments) will consider this relationship in the modelling by specifying patient as a random factor.

If the input data is log-transformed then LSMean and LSMeans differences between treatment groups will be back-transformed to their original scale for descriptive purposes. After subtracting the geometric mean of the log baseline values, the back-transformed LSMeans will correspond to the percentage change from baseline, while the back-transformed LSMeans differences will correspond to the ratio of percentage changes from baseline.

Time to event variables (e.g., time to first fracture) will be analysed using Kaplan-Meier methods, and quartiles for the median time to event will be presented together with their 95% confidence intervals.

Count variables (e.g number of new fractures) will be analysed using Poisson regression. Analyses will include treatment and randomisation as fixed effects and the logarithm of the duration of exposure to study medication will be included as an offset variable in the model. In case over dispersion is a concern, the negative-binomial regression model will be applied instead.

For binary outcomes the proportion of patients with a response will be summarised and compared between treatment groups using Chi squared test.

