8.5.3.3.1 Vertebral Fractures

For all vertebral assessments the X-ray scans will be used as source.

The number and proportion of patients with a new vertebral fracture and new or worsening vertebral fracture will be summarised by treatment group throughout the treatment period (at each visit). In addition, a P-value for the comparison between each group will be provided using a Chi squared test.

The total number of new vertebral fractures and new or worsening vertebral fractures per patient during the treatment period will be compared between each treatment group using a poisson regression model as described in section 8.5.1. An estimate of the ratio of new vertebral fractures and new or worsening vertebral fractures between treatment groups will be presented together with a two-sided 95% confidence interval and P-value.

For patients that have a vertebral fracture a shift table of the change in fracture grade will be presented. The number and percentage of patients with each level of change (from worst baseline grade to worst post-baseline grade) will be displayed.

Finally the total sum of vertebral fracture grades will also be analysed via ANCOVA in the same manner as the change from baseline in Tr.vBMD (radius) on HRpQCT (see Section 8.5.2.1).

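### The chi-squared and log-rank fracture tests omit the OI-type randomisation stratum, so they are conservative if OI type predicts fracture

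*SAP*

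**What the plan says.** SAP 3.2.1 says that "the randomisation scheme will be stratified according to the Sillence Clinical Classification of OI type into 2 groups (Type I or III/IV"). Protocol 8.2 agrees.

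The general rule in SAP 8.5.1 is: "For binary outcomes the proportion of patients with a response will be summarised and compared between treatment groups using Chi squared test". It is applied in two places:

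- SAP 8.5.3.3.1, for patients with a new, or a new or worsening, vertebral fracture: "a P-value for the comparison between each group will be provided using a Chi squared test".
- SAP 8.5.3.9, for peripheral, vertebral, non-vertebral, long-bone and any fracture, at Month 12, by quarter and cumulatively by month: "For each rate, a P-value for the comparison between each group will be provided using a Chi squared test".

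For time to first fracture, SAP 8.5.3.9 adds: "Comparisons between treatment regimens will be performed by means of the log-rank test". None of these sentences names a stratification term. Protocol 11.3.1 also specifies chi-squared tests for fracture rates without a stratum. In SAP 8.5.3.9, OI type enters only the descriptive part, where results "will be summarised by treatment group and OI type at Month 12".

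Other models do carry the stratum. In SAP 8.5.1 the ANCOVA has treatment, randomisation stratum and baseline. The Poisson model, or its negative-binomial alternative, lists treatment and randomisation as fixed effects, which I read as the randomisation stratum. SAP 8.5.3.3.1 uses the count model for the number of new, and of new or worsening, vertebral fractures, and the ANCOVA for the sum of vertebral grades.

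**The concern.** Stratified allocation balances the arms on OI type. If fracture risk differs by type, the difference between arms then varies less than an unstratified test assumes, because that test's variance still includes the between-type part. The p-values tend to be too large and some precision is lost.

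Where balance by type is not assured, the problem is different: the unstratified test cannot separate a difference in case mix from a treatment difference. SAP 8.5.3.9 runs the fracture analyses on the FAS, the Non-restricted FAS and the PP population. PP exclusions can disturb balance. The Non-restricted FAS also includes former placebo participants who were reassigned to open-label treatment rather than randomised to it.

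The plan is also inconsistent with itself: in SAP 8.5.3.3.1, new vertebral fracture is tested with the stratum as a count and without it as yes/no. No reason is given.

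**Working it through.** **Inputs from the documents.** 25 participants per blinded arm (SAP 5); two strata (SAP 3.2.1); two-sided 5% tests with no multiplicity adjustment for secondary endpoints (SAP 8.1.4). The documents give no fracture rate, event count, stratum mix or power for the fracture comparisons, so there is no planned figure to reproduce.

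**Assumed inputs.** 12-month fracture risk of 20-30% in Type I and 50-70% in III/IV, with III/IV making up 25-40% of participants.

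**Formulas.** With stratum share w, stratum risk p and overall risk pbar, and strata balanced by design:

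- ratio = Σ w·p(1−p) / [pbar(1−pbar)]
- true size of a nominal 5% test = 2·[1 − Φ(1.96/√ratio)]
- extra patients = 1/ratio − 1

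| Type I risk | III/IV risk | III/IV share | Ratio | True size | Extra patients |
|---|---|---|---|---|---|
| 30% | 50% | 25% | 0.2200/0.2275 = 0.967 | 4.6% | 3% |
| 30% | 50% | 40% | 0.2260/0.2356 = 0.959 | 4.5% | 4% |
| 30% | 60% | 25% | 0.2175/0.2344 = 0.928 | 4.2% | 8% |
| 20% | 70% | 25% | 0.1725/0.2194 = 0.786 | 2.7% | 27% |
| 20% | 70% | 40% | 0.1800/0.2400 = 0.750 | 2.4% | 33% |

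Example, last row: pbar = 0.6×0.20 + 0.4×0.70 = 0.40, so the variance used is 0.40×0.60 = 0.24. The within-stratum variance is 0.6×0.16 + 0.4×0.21 = 0.18.

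The simple 1/ratio figure applies at 50% power. At 80% power the factor is [(1.96 + 0.84√ratio) / (2.80√ratio)]², which gives about 2% at ratio 0.967 and 23% at 0.750.

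**Simulation at the planned size.** 25 versus 25, exact stratum balance, III/IV share 20% or 40%; 200,000 runs for chi-squared and CMH, 10,000 for log-rank. Power is at an assumed odds ratio of 0.25.

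| Risk, Type I / III/IV | Chi-squared size | CMH size | Chi-squared power | CMH power | Log-rank size | Stratified log-rank size |
|---|---|---|---|---|---|---|
| 30/30 | 5.4% | 4.9-5.0% | 46-47% | 45% | 4.8-5.3% | 4.9-5.4% |
| 20/40 | 4.8-5.0% | 4.8-5.0% | 38-42% | 38-42% | 4.5-5.0% | 5.1-5.3% |
| 20/50 | 4.2-4.5% | 4.7-5.1% | 38-44% | 40-45% | 3.7-4.0% | 4.8-5.1% |
| 15/60 | 2.9-3.4% | 4.8-5.2% | 30-38% | 35-43% | 2.4-2.9% | 4.9-5.2% |
| 10/70 | 1.4-1.8% | 4.9-5.1% | 20-28% | 29-40% | 1.1-1.5% | 5.6-6.2% |

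The 5.4% at 30/30 arises where OI type has no effect, so it is small-sample behaviour of the chi-squared test and not a consequence of ignoring the stratum. Under simple instead of stratified randomisation the chi-squared size stays at 5.3-5.5% in all five risk settings, which confirms that stratified allocation is what makes the test conservative. For log-rank power at an assumed hazard ratio of 0.35, stratifying moves 28-34% to 29-35% at 20/40 and 25-35% to 30-42% at 15/60.

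**Imbalance, illustrated.** Suppose 24% of one arm and 36% of another are III/IV, with risks of 20% and 60% (all assumed). The spurious difference is (0.36 − 0.24) × (0.60 − 0.20) = 0.048, about 5 percentage points. A chi-squared test leaves this in; a stratified analysis removes it.

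**The case against.** The case against runs as follows. These are secondary endpoints without multiplicity control, and the sample size was set on radial Tr. vBMD. A conservative test does no harm to validity. The size of the effect rests on risks that the documents do not give; at 20/40 and 20/50 the power change from CMH is at most about 2 points. At 25 per arm, power stayed below 50% in every setting tried, stratified or not. The split by OI type in SAP 8.5.3.9 would make imbalance visible, and the chi-squared test is what the protocol specifies. Finally, stratifying is not free: with five fracture categories tested by quarter and by month, many strata will be sparse, and the asymptotic stratified log-rank test ran at 5.6-6.2% in the 10/70 setting.

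Most of this stands, and it limits the importance of the point. It does not remove it. A descriptive split shows imbalance but does not adjust for it, and sparse strata call for exact or permutation versions, not for leaving the stratum out.

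Three stronger readings are tempting, and the documents support none of them:

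- A reader might infer that every fracture analysis ignores the stratum. The vertebral-count models and the grade-sum ANCOVA include it.
- A reader might infer that the p-values overstate significance. With balanced strata the error runs the other way.
- A reader might infer that fracture is the only clinical outcome at stake. SF-12, EQ-5D-5L and OIQoL-A are also secondary endpoints (SAP 4.2).

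**Conclusion.** The point holds for the chi-squared tests of yes/no fracture outcomes and for the log-rank test of time to first fracture. They omit a factor used in randomisation that the SAP's other models include.

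If OI type predicts fracture, the tests are conservative. Under the assumed risks and stratum mix, within-stratum variance is about 75-97% of the variance used, and a nominal 5% test has a true size of about 2.4-4.6%. The loss is roughly 3-33% more patients on the variance ratio. If the gradient is weak, the gain from stratifying is negligible. In the PP and Non-restricted FAS, where balance by type is not guaranteed, the tests also leave any imbalance unadjusted.

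Stratifying does not make these comparisons well powered. This is a worthwhile improvement to secondary analyses, and it does not affect the primary analysis.

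**What to change.** Before unblinding, amend SAP 8.5.1, 8.5.3.3.1 and 8.5.3.9:

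- Replace the chi-squared test by a Cochran-Mantel-Haenszel test stratified by OI type, exact where cells are sparse, with a stratum-adjusted risk difference and its confidence interval.
- Use a log-rank test stratified by OI type, with a permutation version for rare fracture categories.
- Keep the unstratified tests as sensitivity analyses, which preserves the analysis named in Protocol 11.3.1.
- Record the change in SAP 9, which now reports no departures from the protocol.

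No new data are needed, since OI type is already the randomisation stratum. The cost is slightly more analysis work, mainly for the exact and permutation versions and the adjusted intervals, and up to about 2 points of power if OI type turns out not to be prognostic (46-47% to 45% in the 30/30 setting).
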